These interviews will consider and compare views and experiences of the trial and the acceptability of the guided self-help intervention. All interviews will be conducted by telephone or face-to-face in a location of the participants' choice. At interview, a flexible topic guide will be used to ensure primary issues are covered during all interviews, but without dictating data collection, allowing participants to introduce unanticipated issues. Topic guides will be modified as necessary to reflect emerging findings. Therapists delivering the intervention will also be interviewed towards the end of the trial to illuminate the perceived effectiveness and acceptability of treatments and explore any barriers to its uptake outside of the trial. The researcher will use open-ended questioning techniques to elicit participants' experiences and views of key events. The interviews will be conducted by Doctorate in Clinical Psychology Students and part of the project analysis will serve as an academic assignment for their Doctoral studies i.e. the Service Improvement Research Project. The interviewers will introduce themselves as qualitative researchers.

Interviews with participants are expected to last between 45-60 minutes, will be recorded using a digital voice recorder, transcribed and anonymized. Interviews will be face-to-face where possible but if an individual prefers to conduct the interview on the telephone this will be facilitated. Should participants experience psychological distress during the interview, debrief will be offered and the interviewers will ensure that the participant is aware of how to access appropriate support. If during the interview any concerns are raised, the researcher will contact the principal investigator. The interviewers will be offered support from the principal investigator and qualitative research coapplicant.

Sampling

Purposive sampling will select interviewees in order to attempt to capture maximum variation in views and experiences in order that they adequately reflect those of a range of participants. All participants in the trial will be asked if they are willing to be contacted about taking part in a qualitative interview at the time of trial consent. From participants who indicate that they are willing to be contacted, a purposive sample will be drawn in relation to (i) the trial site, (ii) arm of the trial and (iii) sociodemographic variables such as age, gender, ethnicity and socio-economic status (with participants being selected from areas of high and low social-economic deprivation, based on Index of Multiple Deprivation (IMD2007) score (Noble et al., 2008). Interviews will be analysed in batches, and sampling will continue until no new themes are emerging from the interviews. This is likely to include up to twenty four participants (16 from the CBT group and 8 from the TAU) as well as 2-3 therapist interviews.

Qualitative analysis

Interview transcripts will be checked for accuracy and then imported into NVIVO qualitative data analysis software, to aid management and indexing of data. Analysis will begin shortly after data collection starts, will be ongoing and iterative. Analysis will inform further data collection: for instance, analytic insights from data gathered in earlier interviews will help identify any changes that need to be made to the topic guide during later interviews. Thematic analysis (Braun & Clark, 2006), utilising a data-driven inductive approach (Boyzatsis, 1998), will be used to scrutinise the data in order to identify and analyse patterns and themes of particular salience for participants and across the dataset using constant comparison techniques (Charmay, 2006). Transcripts from the participants, therapists' and carer interviews will be analysed separately, with coding frames being developed for each separate phase. A subset of transcripts will be independently double-coded by other members of the research team and compared. Discrepancies will be discussed and resolved to achieve a coding consensus.

Fthics

23. Research Ethics Approval

NHS Research Ethics Approval is to be sought and relevant R&D approvals for the 2 NHS sites.

24. Protocol Amendments

Protocol amendments will be presented to the Study Steering Committee for consideration and will be implemented only when approved by the NHS Research Ethics Committee.

25. Confidentiality

All eligible participants will be allocated a unique coded Participant Identification Number. This number will be used to identify patients throughout the study. Where possible, personal identifiable data will be removed from all collected data and replaced with the PIN, thereby providing a level of pseudo-anonymisation. The code will be kept separately from the data/assessments and will be stored securely in a place with limited access.

All personally identifiable study related information will be stored at the University of Bath. Study related information that is not anonymous (i.e. personally identifying information) will be transferred from the NHS site to the University site digitally via nhs.net email or an encrypted USB.

Study records are required, and the digital information will be printed and securely stored at the University site in a locked filing cabinet.

All study materials/record sheets containing identifiable information such as Consent Forms will be stored separately and securely in a place with limited access.

Audio recordings of assessments for the purposes of inter-rater reliability, or of intervention sessions for supervision, will be taken from NHS premises only via secure electronic means and destroyed immediately once inter-rater reliability/use in supervision is completed.

All local databases will be protected via password protection.

26. Declaration of Interests

There are no conflicts of interest or other declarations to report

[figure not shown]
27. Access to data

Access to data will be restricted to the research team. Participant identifiable data will be accessible only to those directly involved in direct patient contact such as the GP and relevant professionals where there are concerns about safety.

28. Ancillary and post-trial care

Adverse Events aside, should participants wish to receive further treatment for depression following their involvement in the study, information will be provided as to how best to access this.

29. Participant Timeline

30. Schedule of Events

Activity/Event	Completed by	Baseline	GSH Group Each Session	10 weeks (End of intervention)	16 weeks	24 weeks
Permission for	Clinic					
research contact						
Eligibility	Clinic					
Assessment	or RA					
Informed	RA					
Consent Demographics	RA	√				
PHQ-9	Р	٧	٧	V	٧	٧
CIS-R	Р	٧				
BDI	Р	٧		٧	٧	٧
SIGH-D	IA	٧		٧	٧	٧
GAD-7	Р	٧		٧	٧	٧
OCI-R	Р	٧		٧	٧	٧
PANAS	Р	٧	٧	٧	٧	٧
SF-12	Р	٧		٧	٧	٧
EQ-5D-5L	Р	٧		٧	٧	٧
Economic and	Р			٧	٧	٧

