- To develop self-help materials based on NICE recommended psychological principles for the treatment of depression specifically tailored for adults with ASD and training materials to guide therapists in how best to support adults with ASD in the use of the self-help materials
- To find out how acceptable the materials and the intervention are to adults with ASD and therapists using qualitative methods
- To estimate the rate of recruitment for a large-scale randomised controlled trial (RCT)
- To estimate the retention rates to inform the RCT, particularly the sample size calculation
- To identify the most appropriate outcome measure for the large-scale RCT

Methods: Participants, Interventions, Outcomes

8. Development of the Intervention

The intervention will be developed by 2 clinical psychologists (AR & SB) with training and accreditation in Cognitive Behaviour Therapy (CBT). AR has experience and expertise in adapting CBT interventions for people with Autism. SB has experience and expertise in developing CBT treatments for depression and training IAPT practitioners. The intervention principles have been clearly defined within the background of Behavioural Activation for Depression and the manner in which these will be delivered to adults with Autism via guided self-help (i.e. adapted for Autism) have been clarified. The adaptations are based on principles outlined in the NICE guidance for adults with Autism (CG142, 2012) and previous studies in this area (e.g. Russell et al., 2013).

9. Trial Design

The feasibility study will comprise a Randomised Controlled Trial (RCT) with a nested qualitative evaluation.

Participants will be randomly allocated to Guided Self-help for Depression adapted for Adults with Autism (GSH) or Treatment as Usual (TAU).

Depression will be measured pre-treatment and 10 weeks post randomisation (end of intervention), with additional outcome measurements at 16 and 24 weeks post randomisation.

10. Study Setting

The study will run across 2 NHS sites, Avon & Wiltshire Mental Health Partnership NHS Trust and Northumberland Tyne & Wear NHS Trust.

11. Participants

Inclusion Criteria

 Adults (aged 18 years or over) with a clinic diagnosis of an Autism Spectrum Disorder (ASD) and current depression as measured by a PHQ-9 score ≥ 10 will be eligible to take part.

Exclusion Criteria

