- Participants where intellectual disability is known or suspected will be excluded as the selfhelp materials will not be modified in line with their needs
- o Risk of suicide participants who endorse a score of 3 on Item 9 of the PHQ-9 will be followedup by the lead clinical researcher on each site to assess suicidal risk. Where clinic assessment or research follow-up is indicative that there is a current risk of suicidality such that a lowintensity intervention would not be clinically appropriate, this will be communicated to the relevant health care professional (e.g. referring ASD clinic and/or GP) and the participant will

be excluded from the study. Risk may increase during the study as evidenced by session by session administration of the PHQ-9 for those in the GSH group. If increased risk is identified following review of the case in clinical supervision, the therapist guide and clinical supervisor will discuss whether referral to statutory health services and discontinuation in the study is indicated.

- Participants with a history of psychosis, current alcohol/substance dependence or untreated epilepsy will be excluded
- Participants who report that they have attended > 6 sessions of individual psychological treatment within a CBT framework over the past 6 months will be excluded from the study
- o Participants who are non-English speaking as the intervention takes the form of written materials and therapist discussion which requires a sufficient level of English to access.

12. Recruitment

Patient identification

Participants will be identified by (i) clinicians in the Bristol Adult Autism Service (BASS) within AWP, (ii) 'Everybody Included' within AWP, (iii) clinicians in the Adult Autism Clinic in NTW and (iv) the Autism Spectrum Cohort-UK at Newcastle University.

There are different versions of patient identification according to local clinical and recruitment procedures and these are outlined below.

i) Adult Autism Clinic in AWP

The PHQ-9 is administered as part of pre-clinic screening. Clinicians will identify individuals attending the clinic who meet the eligibility criteria i.e. PHQ-9 score ≥ 10 for the study.

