The therapist will be a 'low intensity' cognitive behaviour therapist or Psychological Wellbeing Practitioner (PWP) i.e. a therapist working at the low intensity step of the care pathway for depression who has knowledge of cognitive behavioural theory of psychological problems and training/experience in delivering manualised interventions. They will not ordinarily have the knowledge and training to develop individualised, formulation driven interventions for psychological problems.

The therapists will be trained in the intervention by AR, SB and an adult with Autism, ideally who is part of the Patient and Public Advisory Group. The training will last 15 hours.

The therapists will receive weekly supervision in the AWP site by AR and NTW site by SB for the duration of the intervention phase of the study. Supervisory cover will be provided via telephone or Skype when required for either site.

The patient can be offered the option of telephone sessions for sessions 6-8.

Comparator

The comparator intervention is Treatment as Usual (TAU). TAU will be carefully recorded in terms of the nature and timing of any intervention received. This will be via the resource use questionnaire. TAU as usual may include:

- 1. No treatment
- 2. Signposting for self-referral to IAPT services
- 3. Autism clinician recommendation to the GP to make a referral to IAPT services
- 4. Clinic or GP referral to secondary care mental health services
- 5. Anti-depressant medication

Concomitant Care

Medication and changes to medication will be recorded.

For participants allocated to GSH, the start of any adjunct psychological intervention (talking therapy) will be delayed for the duration of the intervention. After 10 week assessment, receipt of additional social and psychological interventions will be recorded as part of the follow-up assessments.

15. Outcomes

Measures of depression

- The Patient Health Questionnaire (PHQ-9) (Spitzer et al., (2006)
- o Beck Depression Inventory-II (BDI-II) (Beck et al., 1996)
- O Hamilton Rating Scale for Depression (Hamilton, M.(1960) The Hamilton Depression Rating Scale (HDRS) will be administered according to the Structured Interview Guide for the Hamilton Depression Rating Scale (SIGH-D) (Williams, JBW, 1988). To further consider reliability of this observer rating of depression, consent to record the interview will be sought and/or an additional rater will be present to establish inter-rater reliability

Other Quantitative Outcomes

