Information capable of identifying individuals will be held on the database with passwords restricted to authorised study staff only.

19. Statistical Analysis

For this feasibility study, we will calculate: (1) the proportion of adults with ASD consenting to the study; (2) the proportion completing the baseline assessment and entering the randomised phase; (3) for those in the intervention group, the number of guided self-help sessions attended and the proportion completing 5 or more sessions; (4) the proportion completing follow-up assessments at 10 and 16 weeks post-randomisation. We will also compare the continuous scores on the depression outcome measure between groups. The standard deviation of the outcome will inform the sample size calculation for the large-scale RCT.

Methods: Monitoring

20. Data Monitoring

A Data Monitoring and Ethics Committee will be convened with an independent Chair, and will monitor accumulating trial data during the course of the study and make recommendations to the Trial Steering Committee as to whether there are any ethical or safety issues that may necessitate a modification to the trial protocol.

21. Safety assessments and monitoring

Adverse Events (AE)

The recommendations for defining and reporting adverse events and harm from psychological therapies as outlined by Parry, Crawford and Duggan (2016) will be used in the Adept Study. An Adverse Event (AE) refers to:

- (a) A significant episode during or shortly after treatment (e.g. suicide, suicide attempts, mental health related hospital admissions) which if related to or directly caused by treatment amount to harm or severe harm
- (b) A sustained and clinically significant deterioration i.e. a worsened mental state after therapy is complete, which can include the emergence of new symptoms. For the purposes of the present study this would be reflected in a categorical negative change in scores on 1 or more of the depression measures used in the study across 2 follow-up points
- (c) Report of a negative experience of the psychological intervention and perceived harm on the part of the participant when interviewed for the nested qualitative study.

Serious Adverse Events (SAEs)

A serious adverse event (SAE) is defined as an untoward occurrence that:

- (a) results in death;
- (b) is life-threatening;
- (c) requires hospitalisation or prolongation of existing hospitalisation;
- (d) results in persistent or significant disability or incapacity;

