- (f) is otherwise considered medically significant by the investigator.

The study will monitor the occurrence of any serious adverse event which arises whilst the participant is taking part in the ADEPT trial.

Participants, researchers and clinical staff should notify any adverse event which they believe may have occurred as a result of the trial intervention or the research process. On notification of such an adverse event which may be related to the research process or intervention, a researcher or member of site staff should complete an adverse event report form within 5 working days, paying specific attention to information regarding the nature and timescale of events i.e. when the event started,

were there any specific changes to medication or behaviour preceding the event. Further information should be requested from the participant, clinical team or GP as necessary. A completed form should be securely sent to the Chief Investigator for review and assessment of relatedness and expectedness as follows:

- 1. Confirmation of seriousness (whether the adverse event is an AE or SAE)
- 2. Causality i.e. relatedness of the event to the study intervention, according the following definitions:

Unrelated – where an event is not considered to be related to the study intervention Possibly – although a relationship to the study intervention cannot be completely ruled out, the nature of the event, the underlying disease, concomitant medication or temporal relationship make other explanations possible

Probably – the temporal relationship and absence of a more likely explanation suggest the event could be related to the study intervention

Definitely – Known effects of the study intervention, or based on challenge testing, suggest that study intervention is the most likely cause.

3. Expectedness of the event. Is the event an anticipated event even if the research had not been taking place?

Serious Adverse Event reporting

All SAEs will be reported to the Chief Investigator within 24 hours of awareness of the SAE. All SAEs that occur in relation to the intervention must be recorded, together with data including date of onset and resolution, outcome, severity and causality for the intervention.

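### When suicide risk rises in a GSH participant, the protocol lets staff consider stopping the study rather than stopping GSH, and does not say that follow-up continues

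*Protocol*

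**What the plan says.** The suicide-risk bullet in Protocol section 11 begins as a baseline exclusion and then moves to events after randomisation: "Risk may increase during the study as evidenced by session by session administration of the PHQ-9 for those in the GSH group". If review in clinical supervision confirms increased risk, "the therapist guide and clinical supervisor will discuss whether referral to statutory health services and discontinuation in the study is indicated".

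Other parts of the protocol bear on this:

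- **Concomitant Care:** "For participants allocated to GSH, the start of any adjunct psychological intervention (talking therapy) will be delayed for the duration of the intervention". It continues: "After 10 week assessment, receipt of additional social and psychological interventions will be recorded as part of the follow-up assessments".
- **Section 12, Retention strategies:** loss to follow-up is ordinarily recorded when the agreed contact plan has been completed and contact has not been kept.
- **Section 17 and the Schedule of Events (section 30):** outcomes are collected at 10, 16 and 24 weeks. Nothing is said about participants who have been discontinued.
- **Section 7:** one objective is "To estimate the retention rates to inform the RCT, particularly the sample size calculation".
- **Section 21:** one type of adverse event is a sustained deterioration, shown by "a categorical negative change in scores on 1 or more of the depression measures used in the study across 2 follow-up points". On serious events: "The study will monitor the occurrence of any serious adverse event which arises whilst the participant is taking part in the ADEPT trial".

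**The concern.** Stopping a treatment and leaving a trial are different events, and the rule names the second. Earlier in the same bullet, a participant with unacceptable risk at baseline is excluded from the study, which plainly means the whole trial. Nothing signals that the word has a narrower meaning a few lines later.

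The route exists in one arm only. Its trigger is the session-by-session PHQ-9, which TAU participants do not complete, and the PHQ-9 is itself one of the depression outcomes. Any exits would therefore be one-sided and related to outcome.

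Three things are at stake:

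- Depression scores at 10, 16 and 24 weeks would be missing for some of the GSH participants at highest risk.
- The deterioration event needs two follow-up points, so it could not be assessed for them. Serious-event monitoring tied to taking part could also end early.
- Retention is something this feasibility study exists to estimate. Exits decided by staff would be mixed with true loss of contact.

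**Working it through.** **1. Does the text require or permit leaving the study?** It permits it and does not require it: staff discuss whether it is indicated. The Concomitant Care section shows why only GSH needs to stop. Other talking therapy is held back while GSH runs, so a referral may mean ending GSH. Further interventions are recorded at follow-up anyway, so a referred participant still fits the existing assessments.

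**2. Does another section keep follow-up going?** Sections 12, 17, 21 and 30 and the Concomitant Care section do not say so. The loss-to-follow-up rule in section 12 concerns lost contact, which does not describe a staff decision.

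**3. The plan's own retention figure.** Section 16 gives 75% to 93% for 85% retention. An exact (Clopper-Pearson) interval for 60/70 = 85.7% is 75.3% to 92.9%, which reproduces it.

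**4. Effect on retention.** The protocol gives no number of exits. Assume k = 1 to 5 of the 35 GSH participants, all of whom would otherwise have been followed up. This makes the figures upper limits. Start from 30/35 in each arm.

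| k | GSH retention | Gap to TAU (85.7%) | Overall retention (exact 95% CI) |
|---|---|---|---|
| 1 | 29/35 = 82.9% | 2.9 points | 59/70 = 84.3% (73.6% to 91.9%) |
| 5 | 25/35 = 71.4% | 14.3 points | 55/70 = 78.6% (67.1% to 87.5%) |

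The overall loss is 1/70 = 1.4 to 5/70 = 7.1 points. If the main trial were planned on the lower figure, starting from 85%, recruitment would rise by 0.85/(0.85 − 1/70) − 1 = 1.7% to 0.85/(0.85 − 5/70) − 1 = 9.2%.

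**5. Effect on the depression scores.** Assume a normal model in which the k GSH participants worst on the trigger leave, and the trigger correlates ρ = 0.2 to 0.5 with the later score (also an assumption). With q = k/35 and z = Φ⁻¹(1 − q):

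- m = φ(z)/(1 − q) and v = 1 − zm − m²
- shift in the GSH mean = ρm
- GSH variance = 1 − ρ²(1 − v), pooled over 35 − k GSH and 35 TAU participants

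| k | z | m | v | ρ | Shift (SD) | Pooled SD |
|---|---|---|---|---|---|---|
| 1 | 1.902 | 0.067 | 0.868 | 0.2 | 0.013 | 0.999 |
| 1 | 1.902 | 0.067 | 0.868 | 0.5 | 0.034 | 0.992 |
| 5 | 1.068 | 0.263 | 0.650 | 0.2 | 0.053 | 0.997 |
| 5 | 1.068 | 0.263 | 0.650 | 0.5 | 0.132 | 0.980 |

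A finite-sample simulation (60,000 runs) gave shifts of 0.011 and 0.031 for k = 1 and 0.049 and 0.126 for k = 5.

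Sampling error for comparison:

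- The 95% half-width for 35 against 35 is 1.96 × √(2/35) = 0.47 SD.
- The standard error of an SD from 70 people is 1/√(2 × 68) = 8.6%, against a fall of 0.1% to 2.0%.

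A cruder check fixes the gap D between those who leave and those who stay, so that shift = (k/35) × D. With D = 0.5 to 1.5 SD the shift runs from 1/35 × 0.5 = 0.01 to 5/35 × 1.5 = 0.21 SD. The top value assumes a stronger link than the model, where k = 5 and ρ = 0.5 imply a gap of 0.132/(5/35) = 0.92 SD.

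**The case against.** The best reply is that the phrase is a slip for stopping GSH. The bullet is concerned with whether a low-intensity intervention is suitable. The people who discuss the matter deliver and supervise GSH, and nothing gives them a part in outcome assessment. The schedule applies to everyone, the contact plan in section 12 covers all who consent, and section 16 counts retention over those randomised. This makes the intention uncertain. It does not make the text clear: staff following the sentence as written could end participation, and no other sentence tells them not to.

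The effect on the estimates is also small, and its inputs are assumed. That stands. Participants whose suicide risk makes a low-intensity intervention unsuitable are excluded at baseline, so five exits is a high case. Removing the worst k overstates what case-by-case decisions would do.

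If the main trial kept the same rule, the lower retention figure would be the right one for planning. That is fair. The recruitment increase is an excess only if the main trial keeps such participants in follow-up. Without a separate record, though, the two kinds of loss cannot be told apart.

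On safety, GSH has adverse-event checks at each session. Section 21 also has a route not limited to time on study: "All SAEs that occur in relation to the intervention must be recorded". The net direction of any bias in harm counts is therefore not established. What remains is the deterioration event, which needs follow-up scores.

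Finally, the analysis group could be left to the SAP. Whether visits are offered is a conduct rule for the protocol, and no analysis plan can recover assessments that were never made.

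**Conclusion.** The concern holds as a minor point. Read literally, the rule opens an outcome-related exit from the study in the GSH arm only, and the protocol does not say that follow-up continues. Intent is uncertain, because stopping GSH alone is a plausible reading and no exit is mandatory.

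Under the assumed 1 to 5 exits and correlation of 0.2 to 0.5, the distortion of the GSH mean and of the SD is well inside sampling error; even the cruder 0.21 SD is less than half of the 0.47 SD half-width. The more practical cost is to retention, together with one GSH participant per exit who cannot be assessed for sustained deterioration. The true number of exits is unknown and probably small.

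**What to change.** In Protocol section 11, make the GSH intervention, not the study, the object of discontinuation, and add:

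> Participants who stop GSH for this reason stay in the group to which they were randomised and will be offered the 10-, 16- and 24-week assessments and adverse event monitoring unless they withdraw consent to follow-up. The date and reason will be recorded separately from loss to follow-up.

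The clinical decision and the referral are unchanged. The cost is a minor wording amendment and one CRF field that separates stopping GSH from withdrawing from follow-up. The visits and adverse-event collection are already scheduled for everyone.

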- Obsessive Compulsive Inventory-Revised (OCI-R) (Foa et al., 2002)
- General Anxiety Disorder Questionnaire (GAD-7) (Spitzer et al., 2006)
- Positive and Negative Affect Schedule (PANAS) (Crawford & Henry, 2004)
- Work and Social Adjustment Scale (WSAS) (Mundt et al., 2002)
- o EQ-5D-L (Herdman et al., 2011)
- o SF-12 (Ware et al., 1996)
- Economic evaluation We will pilot data collection on resource use using a questionnaire administered at 10, 16 and 24 weeks to provide information on: use of other primary and community care services (NHS Direct, attendances at walk-in centres, use of community health care services); secondary care related to mental health (number of out-patient visits,

type of clinic, and reason for visit; inpatient stays, length of stay and reason); use of social services and disability payments received; personal costs related to mental health (expenditure on over-the-counter medication, expenditure on prescriptions, travel costs associated with health care visits, loss of earnings, out of pocket expenditure on other services e.g. private counselling or complementary or alternative therapies, child care and domestic help); time off work and unpaid activities. We will also access GP records to provide information on: number of primary care consultations, by type e.g. face-to-face, telephone etc., and who seen; and prescribed medication.

Methods: Data Collection, Management and Analysis

16. Sample Size

This feasibility study will not be powered to detect important clinical differences between intervention and usual care groups. We are proposing to collect data on outcomes that will be used to inform a future large-scale trial. By recruiting a sample of 70 participants with 35 in each randomised group we will be able to decide on the practical issues of conducting the trial and for estimating the standard of the continuous depression outcome with reasonable precision (Teare et al., 2014). Such a number would provide estimates of the completion rates of the intervention and retention rates that would assist in planning the recruitment for a future RCT. For example, if 80% of those randomised to receive the intervention complete guided self-help, the 95% confidence intervals would be 69% and 89%. Similarly, if 85% of those randomised are followed up at 10 weeks, the 95% confidence intervention for the retention rate would be 75% to 93%.

17. Data Collection Methods

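### The 95% confidence interval quoted for the guided self-help completion rate (69% to 89%) corresponds to 70 people, but only 35 are randomised to guided self-help; the exact interval on 35 is 63% to 92%

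*Protocol*

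**What the plan says.** Section 16 of the protocol (Sample Size) says that the study is not powered for clinical differences between the groups. It sets the size at "a sample of 70 participants with 35 in each randomised group" and links that number to practical questions, to estimating the variability of the depression outcome, and to estimating completion and retention rates for planning a later trial.

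Two worked examples of precision follow. The first concerns completion of the intervention: "if 80% of those randomised to receive the intervention complete guided self-help, the 95% confidence intervals would be 69% and 89" per cent. The second concerns retention: "if 85% of those randomised are followed up at 10 weeks", with limits of 75% and 93%. Neither example states its denominator as a number or names the interval method.

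Section 19 (Statistical Analysis), item 3, sets out the matching analysis: "for those in the intervention group, the number of guided self-help sessions attended and the proportion completing 5 or more sessions".

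**The concern.** The completion example is conditional on being allocated to guided self-help. Treatment-as-usual participants are offered no guided self-help sessions and cannot complete them, so they cannot count in the denominator. With equal allocation of 70, that denominator is 35. An interval only 20 points wide around 80% looks too narrow for 35 people and about right for 70.

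In a feasibility study without a power calculation, statements of this kind are what the reader has for judging whether the size is adequate. As written, a reader would conclude that an observed completion rate of 80% makes a true rate below 69% implausible. If the interval really belongs to 70 people, the planned arm cannot support that conclusion, and planning of the later trial would start from an overstated precision for a main feasibility quantity.

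**Working it through.** **Inputs** (Sections 16 and 19 of the protocol)
- Total randomised: 70; guided self-help arm: 35.
- Assumed completion: 80%, so 0.80 × 35 = 28 completers. If all 70 were the denominator, 0.80 × 70 = 56.
- Stated 95% interval for completion: 69% to 89%.
- Assumed retention at 10 weeks: 85% of all randomised; stated 95% interval 75% to 93%.

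**Formula.** The exact (Clopper-Pearson) two-sided 95% interval for x out of n is:
- lower limit = 2.5% quantile of Beta(x, n − x + 1)
- upper limit = 97.5% quantile of Beta(x + 1, n − x)

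**Step 1: reproduce the stated completion interval.** With x = 56 and n = 70, the quantiles of Beta(56, 15) and Beta(57, 14) are 68.7% and 88.6%. These round to the stated 69% and 89%. Holding the rate at 80% and varying n from 20 to 119, the exact limits round to 69% and 89% only for n = 68 to 72.

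**Step 2: test the same method on the retention example.** 0.85 × 70 = 59.5, which is not a whole number. With x = 60, the quantiles of Beta(60, 11) and Beta(61, 10) are 75.3% and 92.9%, matching the stated 75% and 93%. With x = 59 the limits are 73.6% and 91.9%, which do not match. One method with one denominator, n = 70, thus reproduces both intervals.

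**Step 3: use the correct denominator for completion.** With x = 28 and n = 35, the quantiles of Beta(28, 8) and Beta(29, 7) are 63.1% and 91.6%.

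**Step 4: check whether another 95% method gives the stated limits on 28/35.**

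| Method | Lower | Upper |
|---|---|---|
| Exact (Clopper-Pearson) | 63.1% | 91.6% |
| Wilson | 64.1% | 90.0% |
| Agresti-Coull | 63.8% | 90.3% |
| Jeffreys | 64.7% | 90.6% |
| Wald | 66.7% | 93.3% |
| Wald, continuity-corrected | 65.3% | 94.7% |

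The Wald row, for example, is 0.80 ± 1.96 × √(0.80 × 0.20 / 35) = 0.80 ± 0.1325. In every row the lower limit is below 69% and the upper limit is above 89%.

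**Step 5: size of the discrepancy (exact method).**
- Width on 35: 91.56 − 63.06 = 28.5 points.
- Width on 70: 88.61 − 68.73 = 19.9 points.
- Ratio: 28.5 / 19.9 = 1.43, close to the √2 = 1.41 expected when n is halved.
- Lower limit: 63% instead of 69%. Upper limit: 92% instead of 89%.

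**The case against.** The arithmetic is hard to dispute; the objections concern weight and inference.

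- **The figure is only an illustration.** It is introduced as an example at a hypothetical 80%. The protocol sets no target width, no minimum acceptable completion rate and no progression threshold, and it also rests the sample size on estimating the variability of the depression outcome. This stands: no stated criterion fails when the interval widens, and the example should be described as illustrating the precision of the chosen size, not as determining that size. It does not make the figure right. It is one of only two numerical precision statements in the section.
- **The analysis will not inherit the error.** Section 19 already confines completion to the intervention group, so an interval computed from the observed data would use the right denominator. This also stands, and it limits the consequence to the stated planning precision.
- **The use of 70 is inferred.** True: neither the method nor the denominator is given. The inference is strong, because the exact method on 70 reproduces both intervals. The conclusion does not need it in any case, since none of the methods checked gives the stated limits on 35.
- **A different confidence level could explain the figure.** An exact 80% interval on 28/35 is 68.7% to 88.5% and happens to round to the same limits. The text says 95%, so this is no defence.
- **The exact method is pessimistic at the lower end.** Depending on the method, the lower limit on 35 is about 2 to 6 points below 69%. The exact method remains the fair comparison because it is the one that reproduces the protocol's own figures.

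**Conclusion.** The concern holds. The stated 95% interval of 69% to 89% for guided self-help completion is wrong for the planned arm of 35. The exact interval for 28/35 is 63% to 92%. About 70 people in the guided self-help arm alone, twice the planned number, would be needed for the quoted precision.

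This rests on equal allocation of 70 as planned, on 80% being exactly 28 of 35, and on a two-sided 95% level. The choice of method moves the limits by a few points but does not change the conclusion. The retention interval is correct for 60 of 70. The error does not touch the planned analyses, the estimate of the outcome's standard deviation or participant safety.

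**What to change.** In Section 16, restate the completion example with its denominator, for instance: if 28 of the 35 participants randomised to guided self-help (80%) complete it, the exact 95% confidence interval would be 63% to 92%. Name the interval method. Keep the retention limits, but state that they are for both arms combined (n = 70) and give the count they rest on, 60/70, or 85.7%.

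The cost is an edit to one sentence and a short label on the next. The stated precision becomes less favourable. The correction does not itself call for more participants; if the sponsor judges 63% to 92% too wide for planning the later trial, the size of the guided self-help arm would need a fresh justification.
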